7.4.2 Prophylactic Medications

- Prophylactic antibiotics used pre-operatively: yes, no (**Table 15**)
- Prophylactic antibiotics used post-operatively: yes, no (**Table 15**)
- Prophylactic anticoagulation used pre-operatively: yes, no (**Table 15**)
- Prophylactic anticoagulation used post-operatively: yes, no (**Table 15**)

7.4.3 Transfusion or Blood Products

- Estimated amount of blood loss during surgery: <500cc, 500-1000cc, >1000cc (**Table 16**)
- Transfusions or blood products during surgery and/or in the 4 weeks following surgery: yes, no (**Table 16**)
- Hemoglobin used pre-operatively: median, min-max (**Table 16**)

- Hemoglobin used post-operatively: median, min-max (**Table 16**)
- Type of transfusion: red cell concentrations, platelets, other (**Table 16**)
- Total number of units of transfusion of red cell concentrations: median, min-max (**Table 16**)
- Total number of units of transfusion of platelets: median, min-max (**Table 16**)
- Total number of units of other transfusions: median, min-max (**Table 16**)

7.4.4 Surgical Complications

- Intraoperative injury: yes, no (**Table 17**)
- Location of intraoperative injury: bladder, ureter, vein, artery, large bowel, small bowel, nerve injury, other (**Table 17**)
- Admission to hospital for the hysterectomy: yes, no (**Table 17**)
- Admission to intensive care for the hysterectomy: yes, no (**Table 17**)
- Days in intensive care for the hysterectomy: median, min-max (**Table 17**)
- Days from admission to hospital for the hysterectomy to discharge: median, min-max (**Table 17**)
- Destination of discharge: home, etc. (**Table 17**)

7.4.5 Results of Tumor Assessment after Hysterectomy

- Cervical cancer detected in hysterectomy specimen: yes, no (**Table 18**)
- Histologic tumour type: squamous, adenocarcinoma, adenosquamous (**Table 18**)
- Histologic grade: 1, 2, 3, not assessable (**Table 18**)
- Depth of stromal invasion: median, min-max (**Table 18**)
- Location of stromal invasion: inner half cervical wall, outer half cervical wall (**Table 18**)
- Horizontal spread/greatest diameter: median, min-max (**Table 18**)
- Lymphovascular invasion: yes, no, undetermined (**Table 18**)
- Resection margins involved: yes, no (**Table 18**)
- Presence of associated intra-epithelial lesion: yes, no (**Table 18**)
- Presence of tumour in the parametrium: yes, no, not applicable (**Table 18**)
- Location of tumour in the parametrium: in continuity with tumour, in lymphovascular space, in parametrial lymph node (**Table 18**)

7.4.6 Sentinel Node Mapping and Lymph Node Dissection

- Success of protocol-defined sentinel node mapping: yes, no, not applicable (**Table 19**)
- Reason for unsuccessful protocol-defined sentinel node mapping: technical reasons, patient refusal, allergy to blue dye, other reason (**Table 19**)
- Technique for sentinel node mapping: laparoscopic, open (**Table 19**)
- Pelvic node dissection done: yes, no (**Table 19**)
- Technique of pelvic node dissection: laparoscopic, open (**Table 19**)
- Para aortic lymph node dissection done: yes, no (**Table 19**)
- Technique of para aortic lymph node dissection: laparoscopic, open (**Table 19**)

7.4.7 Results of Sentinel Lymph Nodes Assessment and Non-Sentinel Lymph Nodes Assessment

For each of the lymph node sites assessed, the following information will be summarized for both sentinel and non-sentinel assessment:

- Number of nodes removed: median, min-max (**Table 20**)
- Number of metastatic nodes detected: median, min-max (**Table 20**)
- Size of largest metastasis: <0.2 mm, 0.2-2.0 mm, >2.0 mm (**Table 20**)
- Presence of extracapsular invasion: yes, no (**Table 20**)

7.4.8 Results of Assessment of Extraperitoneal Tissue Other Than Lymph Node and Extra-Pelvic Tissue

- Disease in extraperitoneal tissue other than lymph nodes: yes, no (**Table 21**)
- Location of disease in other extraperitoneal tissue: fallopian tube, parametrium, ovary, peritoneum, vagina, other (**Table 21**)
- Disease in extra-pelvic tissue: yes, no (**Table 21**)
- Location of disease in extra-pelvic tissue: omentum, abdominal organs, peritoneal disease, lung, other (**Table 21**)

7.4.9 Adjuvant Treatment within 4 Weeks after the Hysterectomy

- Patients planned to receive adjuvant radiation/chemotherapy therapy: yes, no (**Table 22**)
- Reason for the plan of adjuvant radiation/chemotherapy treatment: lesion size>2cm, positive margins in the hysterectomy specimen, etc. (**Table 22**)
- Patient received chemotherapy therapy: yes, no (**Table 22**)
- Drug name and dose for each chemotherapy (**Table 22**)
- Patient received radiotherapy Assessment (**Table 22**)
- Type of radiotherapy: external radiotherapy, boost radiotherapy, brachytherapy (**Table 22**)
- Total number of fractions and total dose for each type of radiotherapy (**Table 22**)

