9.0 EVALUATION AFTER PROTOCOL AND NON-PROTOCOL TREATMENT

All patients entered on study must be evaluated according to the schedule outlined in Appendix I with documentation submitted according to the schedule in Appendix IV. The schedule for evaluation after protocol commences as follows:

1. Patients completing simple or radical hysterectomy as per-protocol: the “end of treatment date” is considered the date of surgery.
2. Patients who do not undergo a hysterectomy: the “end of treatment” is considered the date that the decision was made not to have surgery, or the date of the surgical attempt (if applicable).

Patients are to be seen 4-6 weeks after the end of treatment (as defined above) and then again at 3 months after the end of protocol treatment. After this, the visits are q3 monthly for year one, q4 monthly for year two, q6 monthly for year three then q12 months until death or trial completion. At follow up patients will be assessed for local pelvic disease, extra pelvic relapse, and for treatment morbidity. Data collected at each post-treatment follow-up after the end of treatment will include documentation of adverse effects of surgery, status of disease and details of any new post protocol anticancer treatments delivered.

Patients agreeing to inclusion in the Quality of Life and Sexual Health components will complete questionnaires at 3 months, 6 months, 12 months, 24 months, 36 months from end of treatment and at disease recurrence. Patients from Canada, the UK and France agreeing to inclusion in the Health Economics component will complete questionnaires at each follow-up visit from the end of treatment (until disease recurrence) and at the time of disease recurrence. Additional evaluations required at these visits include general performance status, patient weight and Resource Utilization Assessment.

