APPENDIX IV - DOCUMENTATION FOR STUDY

Follow-up is required for patients from the time of randomization and will apply to all eligible patients.

This trial will use a web-based Electronic Data Capture (EDC) system for all data collection except the quality of life questionnaire, sexual health questionnaire and the health economics questionnaire. For details of accessing the EDC system and completing the on-line Case Report Forms please refer to the “CCTG EDC Generic Data Management Guidebook” posted on the CX.5 area of the CCTG web-site (www.ctg.queensu.ca).

The electronic CRFs to be used in this trial, through the EDC system, are as follows:

Electronic Folder	Required	To be completed electronically	De-Identified Supporting Documentation Required ¹
Eligibility Checklist	Prior to randomization	At the time of randomization	
Baseline Report	Prior to protocol surgery	Within 6 weeks after randomization	
 • Consent form signature pages (Canadian patients only) • Copies of pathology reports (from initial diagnosis and LRP review) and radiology reports² • PROs³
LEEP/cone/biopsy Checklist			
Surgery Report	4-6 weeks after protocol surgery	Within 8 weeks after surgery	
 • Operative report • Pathology report • Photograph of hysterectomy specimen for surgical QA⁴ • Lymphocintogram and photographs for SN mapping QA⁵
Adjuvant Therapy Report	Upon the completion of adjuvant therapy	Within 8 weeks after the completion of adjuvant therapy	--
Follow-Up Report	Year One – q 3 monthly ⁶ Year Two – q 4 monthly Year Three – q 6 monthly Then q 12 months until study closure. ⁷	Within 8 weeks of the visit date	
 • Pelvic exam notes • Radiology reports (if done) • Pathology/cytology/surgical reports (if done) • PROs³
Recurrence Report	At the time of first pelvic and/or extra-pelvic disease recurrence	Within 8 weeks of the date of recurrence	
 • Pelvic exam notes • Radiology reports (if done) • Pathology/cytology/surgical reports (if done) • PROs³
Short Follow-up Report	q 6 monthly from the date of the most recent recurrence	Within 8 weeks of the visit date	
 • Pelvic exam notes (if done) • Radiology reports (if done) • Pathology/cytology/surgical reports (if done)
Death Report	At the time of patient death	Within 8 weeks of patient death	Autopsy report (if done)

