7.7 Other Anti-Cancer Treatments and Tobacco Smoking History During Follow-up

Patients may receive surgical, systemic or radiation treatments for cervical cancer other than the protocol surgery and adjuvant treatments given 4 weeks within the protocol surgery treatment or smoke tobacco during the follow-up.

- Any surgery/procedure given 4 weeks after the surgery but before the first pelvic recurrence (reported on Follow Up Report) : yes, no (**Table 39**)
- Type and reason for surgery/procedure given 4 weeks after the surgery but before the first pelvic recurrence (reported on Follow Up Report) (**Table 39**)
- Any surgery/procedure given after the first pelvic recurrence (reported on Short Follow Up Report): yes, no (**Table 39**)
- Type and reason for surgery/procedure given after the first pelvic recurrence (reported on Short Follow Up Report) (**Table 39**)
- Any other anti-cancer treatment given 4 weeks after the surgery but before the first pelvic recurrence (reported on Follow Up Report): yes, no (**Table 40**)
- Type and treatment name or site for other anti-cancer treatment given 4 weeks after the surgery but before the first pelvic recurrence (reported on Follow Up Report) (**Table 40**)
- Any other anti-cancer treatment given after the first pelvic recurrence (reported on Short Follow Up Report): yes, no (**Table 40**)

- Type and treatment name or site for other anti-cancer treatment given after the first pelvic recurrence (reported on Short Follow Up Report) (**Table 40**)
- Smoked tobacco 4 weeks after the surgery but before the first pelvic recurrence (reported on Follow Up Report): yes, no (**Table 41**)
- Smoked tobacco after the first pelvic recurrence (reported on Short Follow Up Report): yes, no (**Table 41**)

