Note: Size of largest metastasis and extracapsular invasion are not applicable for sentinel lymph node assessment of pelvic NOS left and pelvic NOS right sites.

Table 21: Results of Assessment of Extrauterine Tissue Other Than Lymph Node and Extra-Pelvic Tissue

Dataset: All Treated Patients		
	Number of patients (%)	
	Simple Hysterectomy N = ***	Radical Hysterectomy N = ***
Disease in extrauterine tissue other than lymph node		
No	**(**)	**(**)
Yes	**(**)	**(**)
Location of disease in other extrauterine tissue		
Fallopian Tube	**(**)	**(**)
Parametrium	**(**)	**(**)
...	**(**)	**(**)
Disease in extra-pelvic tissue		
No	**(**)	**(**)
Yes	**(**)	**(**)
Location		
Omentum	**(**)	**(**)
Abdominal Organs	**(**)	**(**)
Peritoneal Disease	**(**)	**(**)
Lung	**(**)	**(**)
...	**(**)	**(**)

Table 22: Adjuvant Treatment Within 4 Weeks After the Hysterectomy

Dataset: All Treated Patients		
	Number of patients (%)	
	Simple Hysterectomy N = ***	Radical Hysterectomy N = ***
Planned to receive adjuvant radiation and/or chemotherapy		
Yes	**(**)	**(**)
Treatment Planned		
Radiation alone	**(**)	**(**)
Chemotherapy alone	**(**)	**(**)
Radiation and Chemotherapy	**(**)	**(**)
No		
Reason for not to receive adjuvant treatment	**(**)	**(**)
Lesion size > 2cm	**(**)	**(**)
Extra pelvic spread	**(**)	**(**)
...	** (**)	** (**)
Received Adjuvant Chemotherapy		
No	**(**)	**(**)
Yes	**(**)	**(**)
Chemotherapy treatment		
Drug name 1		
Dose (unit)		
N	**	**
Mean (SD)	** (**)	** (**)
Median (Min-Max)	** (**_**)	** (**_**)
...		
Received adjuvant radiotherapy		
No	**(**)	**(**)
Yes	**(**)	**(**)
Type of radiotherapy		
External radiotherapy	**(**)	**(**)
Boost radiotherapy	**(**)	**(**)
Brachytherapy	**(**)	**(**)
Total dose of external radiotherapy (cGy)		
N	**	**
Mean (STD)	** (**)	** (**)
Median (Min-Max)	** (**_**)	** (**_**)
Total dose of boost radiotherapy (cGy)		
N	**	**
Mean (STD)	** (**)	** (**)
Median (Min-Max)	** (**_**)	** (**_**)
Total dose of Brachytherapy (cGy)		
N	**	**
Mean (STD)	** (**)	** (**)
Median (Min-Max)	** (**_**)	** (**_**)

Table 23: Other Surgeries/Procedures Within 4 Weeks After Hysterectomy

Dataset: All Treated Patients		
	Number of patients (%)	
	Simple Hysterectomy N = ***	Radical Hysterectomy N = ***
Patients received other surgeries/procedures within 4 weeks after hysterectomy		
No	**(**)	**(**)
Yes	**(**)	**(**)
Surgery/Procedure 1		
Reason 1	**(**)	**(**)
Reason 2	**(**)	**(**)
...	**(**)	**(**)
.....		

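### The SAP confines adjuvant treatment to the 4 weeks after hysterectomy, a limit the protocol does not set, so Table 22 understates received adjuvant treatment and no table gives the full adjuvant rate by arm

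*SAP*

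**What the plan says.** **SAP.** Section 7.4.9 is headed "Adjuvant Treatment within 4 Weeks after the Hysterectomy", and the shell is titled "Table 22: Adjuvant Treatment Within 4 Weeks After the Hysterectomy". Under that heading come whether adjuvant treatment was planned and why, whether chemotherapy or radiotherapy was received, drug and dose, type of radiotherapy, and total fractions and dose. No source form is named.

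Section 7.7 repeats the limit in body text. It covers treatments "other than the protocol surgery and adjuvant treatments given 4 weeks within the protocol surgery treatment". Its pre-recurrence item for Table 40 is "Any other anti-cancer treatment given 4 weeks after the surgery but before the first pelvic recurrence", taken from the Follow-Up Report. Both tables use the All Treated set, by surgery received.

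**Protocol.** Section 8.3 leaves adjuvant radiation-based therapy to the treating physician under local policy, with recording on case report forms and no time limit. Section 9.0 takes the surgery date as the end of treatment for women who complete hysterectomy, and says: "Patients are to be seen 4-6 weeks after the end of treatment". Appendix IV requires an Adjuvant Therapy Report "Upon the completion of adjuvant therapy", entered within 8 weeks of that point. Its note 6 starts the first Follow-Up Report period at the 4-6 week visit.

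**The concern.** The SAP defines adjuvant treatment by a calendar window, whereas the protocol defines it by clinical decision and gives it its own form. The two definitions agree only for courses that start and finish within 4 weeks of surgery.

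A complete count by arm matters for interpretation. Post-operative pelvic treatment can influence pelvic recurrence and brings its own toxicity. Protocol 2.5.1 cites worse long-term quality of life after surgery plus radiation than after surgery alone. Protocol 2.5.2 names post-operative adjuvant treatment among the differences that complicated earlier comparisons of sexual outcomes. The adverse-event tables cover only events related to surgery (SAP 7.6.1), so they do not stand in for adjuvant exposure. If use differs between arms, readers need a full table to judge whether it contributed to the recurrence or patient-reported results.

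**Working it through.** The plan gives no figure to reproduce, because no document states an adjuvant rate or a time from surgery to adjuvant start. The check is to follow possible courses through the planned tables as worded.

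| Course | Table 22 | Table 40, pre-recurrence rows |
|---|---|---|
| Starts and ends by week 4 | Included in full | Not applicable |
| Starts by week 4, continues after | Included, but the dose within the window is not the full-course total | Later part only, if on the Follow-Up Report |
| Starts after week 4, before the first visit | Outside the window | Starts before the first Follow-Up Report period opens, so entry is uncertain |
| Starts after the first visit, on the Follow-Up Report | Outside the window | Included as other treatment |
| Starts after week 4, on the Adjuvant Therapy Report only | Outside the window | Not on the named source form |

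The third row arises because the visit may be as late as week 6, leaving a gap of up to 6 − 4 = 2 weeks between the end of Table 22's window and the start of the first follow-up period.

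**What Table 40 can show.** Its shell has rows for systemic therapy by treatment, radiotherapy by site, and other. It has no dose, fractions, reason or adjuvant label. Later adjuvant courses cannot be picked out of it and added to Table 22.

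**Are later starts plausible?** Protocol 8.2 does not allow frozen section of sentinel nodes unless a node looks metastatic, and 8.2.2 places ultrastaging on final pathology. Some findings that prompt adjuvant therapy will therefore emerge only after surgery. This makes later starts plausible but does not say how common they are.

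**How far the share depends on timing.** Assume, purely for illustration, a lognormal time to adjuvant start with median m weeks and log-scale standard deviation σ. Then P(start > 4 weeks) = 1 − Φ((ln 4 − ln m)/σ). For m = 6 and σ = 0.4, (1.386 − 1.792)/0.4 = −1.01, which gives 0.84. With σ from 0.25 to 0.6:

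| Assumed median start (weeks) | Share starting after week 4 |
|---|---|
| 2 | 0-12% |
| 3 | 12-32% |
| 4 | 50% |
| 5 | 65-81% |
| 6 | 75-95% |
| 8 | 88-100% |

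The share runs from almost nothing to almost all, depending on a median that neither document gives.

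**The case against.** The best defence is that 4 weeks is a loose label for the immediate post-operative forms and not a filter. SAP 7.6.1 describes Surgery Report adverse events as falling within 4 weeks, although Appendix IV requires that form at 4-6 weeks. None of the items in 7.4.9 carries a date limit, and a request for total dose reads like full-course data. This is a fair reading of the heading alone. It does not explain 7.7, where the same limit is used in body text to decide what counts as other treatment. A programmer following both sections would apply the cut.

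Three further points stand:

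- Table 22 also reports planned adjuvant treatment and its type, so a difference in intention would be visible whatever the start date. The mitigation is partial because a plan is not treatment received. In addition, the shell lists reasons for not receiving treatment where 7.4.9 asks for reasons for the plan.
- Later courses have a route into Table 40, since Protocol 9.0 has new anti-cancer treatment recorded at follow-up. They are relabelled, and are lost only if recorded solely on the Adjuvant Therapy Report, which no passage says will happen.
- Adjuvant therapy is neither an event nor a censoring reason in SAP 7.5.1, so the primary analysis does not change.

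A reader might infer that most adjuvant treatment falls outside Table 22, that the table would be nearly empty, or that it would conceal an imbalance. The documents support none of these: they give no time to start, and nothing ties the start to the 4-6 week visit.

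A reader might also apply node-positivity rates to 350 women per arm and compare the result with the 14 pelvic recurrences in SAP 2.1. That comparison fails. Protocol 2.1.1 gives 5% as an upper bound for low-risk disease, and the 8.3% in Protocol 2.2.3 is 5 of 60 women in one study. The 14 recurrences are a total across the trial at a pre-final date. SAP 7.5.1 also counts women found at surgery to have more advanced pelvic disease as relapsed on that date, so node-positive women may already be events.

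**Conclusion.** The point holds as a defect in descriptive reporting. Read as written, SAP 7.4.9, Table 22 and 7.7 understate received adjuvant treatment to the extent that courses start or continue after week 4, and no table gives the full adjuvant rate by arm. The size cannot be quantified from the documents. The primary estimate, the margin and the non-inferiority decision are unaffected. What is weakened is the reader's ability to interpret differences in recurrence, toxicity and patient-reported outcomes. The conclusion assumes that the 4-week limit will be programmed as stated; if the sponsor means it only as a label, the SAP should say so and name the source form.

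**What to change.** - In SAP 7.4.9 and Table 22, delete the 4-week limit. Source the table from the Adjuvant Therapy Report, plus any adjuvant treatment on the Surgery Report, whatever the start date, with full-course dose. SAP 7.5.1 calls this form the Adjuvant Treatment Report; use one name.
- Do not restrict the table to treatment before first recurrence, because that could drop women whom 7.5.1 counts as relapsed at surgery.
- Align 7.7, and define Table 40 as anti-cancer treatment not recorded as adjuvant.
- Reconcile the reason rows in the Table 22 shell with 7.4.9.
- As a useful low-cost addition, show received adjuvant treatment by randomized arm for all intention-to-treat patients. The All Treated set requires a hysterectomy, so it omits women whose operation was abandoned (Protocol 8.1).

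The cost is a small amount of SAP and table-shell rework. The form already exists, so no new data collection is needed.

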7.4.10 Other Surgeries/Procedures within 4 Weeks after the Hysterectomy

- Patients received other surgeries/procedures within 4 weeks after the hysterectomy: yes, no (**Table 23**)
- Type of the surgery/procedure and reason of surgery/procedure (**Table 23**)

7.5 Efficacy

7.5.1 Pelvic Recurrence Rate at 3 Years

The pelvic recurrence rate at 3 years, the primary endpoint of the study, will be estimated by 1-the Kaplan-Meier estimate for the probability of pelvic relapse free survival (PRFS) at 3 years, where PRFS is defined as the time from randomization (as recorded in Centralized Randomization File) to the time when a recurrence within the pelvic field was first documented (as recorded in Pelvic Recurrence Section in Recurrence Report). Patients found to have more advanced stages of cervical cancer on sentinel node mapping, pelvic node dissection or other intraoperative findings consistent with pelvic disease will be considered to have pelvic disease relapse as of the date of the surgical procedure. Patients who have a relapse outside of the pelvic

field documented or die before the documentation of a pelvic relapse will be censored at the time of first documented extra-pelvic relapse (as recorded in Extra-pelvic Recurrence Section in Recurrence Report) or death (as recorded in Death Report). The pelvic relapse free survival of patients who are alive without any relapse will be censored at the last disease assessment (randomization date, date of surgery in Surgery Report, date of physical exam in Surgery Report, date of last contact in Adjuvant Treatment Report, date of Attendance/Last Contact in Follow-up Report and Short Follow-up Report, date of last patient contact in Lost to Follow Up Report, date of consent withdrawal in Withdrawal of Consent Report, whichever comes the last).

A summary of patients who have pelvic recurrence and sites of the pelvic recurrence will be provided (**Table 24**).

The pelvic recurrence rate at 3 years will be calculated for each arm as well as the difference in pelvic recurrence rates at 3 years between simple hysterectomy to radical hysterectomy. The upper limit of a one-sided 95% confidence interval for the difference will be calculated based on the Greenwood estimate for the variance of the estimated 3-year PRFS (**Table 25**). The non-inferiority of simple hysterectomy to radical hysterectomy will be claimed when this upper limit is lower than or equal to 4%.

The primary analysis will be performed on all intention-to-treat patients and a sensitive analysis will additionally be conducted for all per-protocol patients defined in Section 6 based on arms they are treated (**Table 25**).

